#### **3.3.12.8 Ancillary analyses**

Additional ancillary interim analyses will be performed on blinded, de-identified data by [name] as part of her doctoral dissertation. [name] is completing her training toward a PhD in clinical psychology at Palo Alto University (PAU), and is a member of PAU's Early Intervention Clinic clinical research laboratory, which provides and evaluates evidence-based treatments to prevent trauma-related problems in recently traumatized individuals. As part of this research laboratory, [name] is examining the effects of trait self-compassion on trauma-related guilt cognitions. Blinded, de-identified scores on the SCQ, Self-Compassion Scale Short-Form (SCS-SF), and number of self-reported drinking days will be shared with [name] to allow her to assess the following aims:

Aim 1) To examine the relationships between self-reported drinking days and self-compassion in the context of a psilocybin-facilitated MET program following two drug administration sessions (either psilocybin or placebo), Aim 2a) To examine within-person, pre-post intervention changes in self-reported drinking days in the context of a medication-facilitated MET program, Aim 2b) To examine within-person, pre-post intervention changes in self-reported self-compassion in the context of a medication-facilitated MET program, Aim 2c) To examine whether these within-person, pre-post intervention changes in self-reported drinking days are greater in participants that score above the median on the SCQ than those with SCQ scores below the median score, Aim 2d) To examine whether these within-person, pre-post intervention changes in self-compassion are greater in participants that score above the median on the SCQ than those with SCQ scores below the median score, and Aim 3) To examine whether SCS-SF scores mediate the relationship between SCQ scores and drinking behavior.

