### 3.3 Approach

#### 3.3.1 Design Overview

The proposed investigation is a multi-site (2-4 sites), double-blind, active-controlled trial (n = 180, 90 per group) contrasting the acute and persisting effects of psilocybin to those of diphenhydramine in the context of outpatient alcoholism treatment. During the double-blind phase, participants will receive psilocybin or diphenhydramine in two monthly sessions, with dose for the second session titrated base on response in the first session. Following completion of the double-blind phase of the protocol (at week 38, 34 weeks after randomization) all participants who meet interim safety criteria will be offered an additional session in which psilocybin will be administered, and participants will be followed for an additional 16 weeks. The drug will be administered during 8 hour sessions in an outpatient setting under close medical and psychiatric monitoring. The drug administration sessions will occur in the context of a behavioral intervention consisting of an extended version of Motivational Enhancement Therapy, (Motivational Enhancement Therapy and Taking Action, META), with the addition of standardized preparation before and debriefing and follow-up after the psilocybin administration sessions. Extensive screening and baseline assessment will be completed, including thorough safety screening and assessment of participant characteristics that could potentially moderate treatment response. Within-session and short-term persisting effects will be assessed. Drinking outcomes and changes in several potential mediators of treatment effect, including motivation, self-efficacy, craving, depression, anxiety, and spiritual dimensions of the experience, will be measured for 50 weeks following initial administration of study medication (See Figure 2).

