### 3.3.3.2 Pilot Study Results

Figure 3 illustrates available pilot results by individual through week 8. Participants were 6 men and 4 women, mean age 40.1 (S.D. 10.3), who were concerned about their drinking but not interested in available treatment. Participants had been alcohol dependent for a mean of 15.1 years (S.D. 11.5) and ranged in severity from mild to severe dependence with a mean of 5.0 dependence criteria (S.D. 1.2).

Participants have tolerated psilocybin well in the pilot study. Transient mild headaches have been common during the 24 hours following psilocybin administration, as reported by Johnson et al. [109]. There have been no persisting adverse events that were considered related to the study treatments. Figure 3a shows mean scores on the Mystical Experience Questionnaire (MEQ) total score for the 10 participants receiving 0.3 mg/kg in the first session and 5 participants receiving 0.4 mg/kg in the second session, as well as scores reported at similar doses in normal volunteers by Griffiths et al. [110]. On average, acute effects are lower in magnitude than those seen at comparable doses in normal volunteers. Intensity of effects varied markedly from patient to patient, with MEQ scores ranging from .02 to .77 in the first session, and Hallucinogen Rating Scale (HRS) intensity scores ranging from 0 to 3.5. The mean score for the 0.4 mg/kg dose appears to be lower than that at 0.3 mg/kg. This is probably because the four participants with the strongest response in the first session did not receive 0.4 mg/kg in the second session.

Results (n=9) for the month before and the two months after the first psilocybin session are shown in Figures 3b-3d. Participants showed modest change in drinking behavior during the first month of psychosocial treatment. However, drinking days and heavy drinking days decreased significantly during the month following the first psilocybin session. Changes in drinking were accompanied by modest significant increases in self-efficacy (AASE confidence scale) following the psilocybin session. Importantly, the magnitude of the effects reported during the first psilocybin session (at week 4) is strongly correlated with changes in craving and self-efficacy in the week following the session, and with changes in drinking in the month following the session. In addition, changes in craving and self-efficacy at week 5 are correlated with changes in drinking during weeks 5-8 relative to weeks 1-4.

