### 3.3.10 Measures

Measures are listed in Table 1 below, organized by domain.

Table 1. Assessment Schedule		Scr.	BL	W04	W05	W08	W09	W12	W24	W36	W38	W39	W42	W54
Medical evaluation	History and physical, liver function tests, complete blood count, Chem 7, U/A, serum pregnancy test, height and weight, medical history intake form	550'												
	ECG		5'							5'				
	Concomitant meds, menstrual calendar		5'	5'	5'	5'	5'	5'	5'	5'	5'	5'	5'	5'
	Urine pregnancy test				5'		5'				5'			
Psychiatric and SUD assessment	Structured Clinical Interview for DSM-IV (SCID), Family History Questionnaire, Folstein MMSE	75'												
Other baseline characteristics	Attentional Resource Allocation Scale, Treatment Goal Form, Demographics Form, Locator Form			15'										
Withdrawal	CIWA-Ar	5'		5'		5'					5'			
Substance use and consequences	Time-line Follow-back, BAC	30'	10'	10'		10'		10'	10'	10'	10'		10'	10'
	Hair/ Nail sample for ethyl glucuronide									5'				
	Urine Drug Screen	5'		5'		5'		5'	5'	5'	5'		5'	5'
	Short Inventory of Problems (past 3 months)		5'					5'	5'	5'				5'
Acute Hallucinogen Effects	5D-ASC, HRS, SCQ, Monitor Rating Scale, Mysticism scale, guesses of medication received, MUSE questionnaire			30'		30'					30'			
Persisting Effects	Mysticism Scale (lifetime), Spiritual Transcendence Scale, Persisting Effects Questionnaire (follow-up)		90'							90'				90'

	only), BMMRS, NEO-PI-3, Schwartz Value Survey													
Motivation	Readiness rulers		5'	5'	5'	5'	5'	5'	5'	5'	5'	5'	5'	
Self-efficacy	Alcohol Abstinence Self-efficacy Scale		10'	10'	10'	10'	10'	10'	10'	10'	10'	10'	10'	
Craving	Penn Alcohol Craving Scale		5'	5'	5'	5'	5'	5'	5'	5'	5'	5'	5'	
Self-Compassion	Self-Compassion Scale (Short Form)		5	5	5	5	5	5	5	5	5	5	5	
Mood/ Anxiety	Ham-D, Ham-A		20'	20'	20'	20'	20'	20'	20'	20'	20'	20'	20'	
	Adverse Events Case Report Form			5'	5'	5'	5'	5'	5'	5'	5'	5'	5'	
Safety	Vital Signs and weight	5'	5'	5'	5'	5'	5'	5"	5'	5'	5'	5'	5'	
	Visual Analog Scales for abuse potential							5'	5'	5'			5'	
Tx satisfact.	Visual Analog Scales							5'					5'	
Assessment Length		185'	175'	110'	55'	110'	55'	85'	85'	170'	110'	55'	75'	170'

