### ***3.3.10.6 Acute and Persisting Hallucinogen Effects***

#### ***3.3.10.6.1 Acute Hallucinogen Effects***

5-Dimensional Altered States of Consciousness Scale (5D-ASC) [130] will be used to quantify acute hallucinogen effects. This scale has 94 items using the visual analog scale format, yielding 5 primary dimensions. The primary dimensions are “oceanic boundlessness,” “anxious ego-disintegration,” “visionary restructuralization,” “acoustic alterations,” and “altered vigilance.”

The Hallucinogen Rating Scale (HRS), developed and validated at the University of New Mexico by Rick Strassman et al. (1994) in studies of intravenous DMT and validated in ayahuasca users [131], will also be administered following each drug administration session. It is being used by the Hopkins and Tucson groups in their psilocybin research, and has been used to assess effects of a wide variety of psychoactive drugs including MDE, methamphetamine, psilocybin, ibogaine, MDMA, ayahuasca, methylphenidate, d-amphetamine, ketamine and mCPP. This 99-item scale has 6 subscales: intensity, somesthesia, affect, perception, cognition, and volition.

The Mysticism Scale will be used to assess “mystical” dimensions of the hallucinogen experience. This 32-item, 3-factor questionnaire has been used in studies of non-drug-induced mystical experiences [132], and has also been used in the psilocybin work of Griffiths et al. (2006).

The States of Consciousness Questionnaire (SCQ) will also be administered. This 100-item questionnaire has been used extensively to measure mystical-type states of consciousness in hallucinogen administration experiments [97, 113, 133-135]. This scale contains the 43 items of the Pahnke-Richards Mystical Experience Questionnaire (MEQ) [97].

A 20-item Monitor Rating Scale [97] will be completed by both therapists at intervals during the psilocybin sessions (every 30 minutes for the first 2 hours, then hourly) to provide objective ratings of participants’ behavior and affect during the session.

A novel Music and Sound Experience (MUSE) questionnaire will be administered at the end of each medication session. The questionnaire contains 20 items that assess the impact the music and sounds played during the medication session had on the quality of the participant's experience.

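### Do the ancillary interim analyses undo the blind by linking SCQ scores to drinking days?

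*Combined protocol and SAP*

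**What the plan says.** Section 3.3.12.8 (Ancillary analyses) states: "Additional ancillary interim analyses will be performed on blinded, de-identified data". The analyst is a doctoral student at an outside university, for whom the document gives no trial role. On what is released it says: "Blinded, de-identified scores on the SCQ, Self-Compassion Scale Short-Form (SCS-SF), and number of self-reported drinking days will be shared". No arm code is listed and no comparison of arms is planned.

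Two aims join the SCQ to drinking. Aim 2c asks whether pre-post changes in "self-reported drinking days are greater in participants that score above the median on the SCQ than those with SCQ scores below the median". Aim 3 is "To examine whether SCS-SF scores mediate the relationship between SCQ scores and drinking behavior". The only timing given is per participant, after both double-blind sessions. There is no calendar date, enrolment count or database lock, and no statement of who sees the results.

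Table 1 in Section 3.3.10 puts the SCQ in the row for acute hallucinogen effects: "5D-ASC, HRS, SCQ, Monitor Rating Scale, Mysticism scale, guesses of medication received, MUSE questionnaire". Section 3.3.10.6.1 adds, "This scale contains the 43 items of the" Mystical Experience Questionnaire (MEQ). Section 3.3.1 describes a "double-blind, active-controlled trial (n = 180, 90 per group").

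Section 3.3.12 refers to a separate SAP for the full analysis description. That text was not available for this check.

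**The concern.** Removing the arm code does not fully blind a file that holds a drug-effect score. With equal arms, splitting the SCQ at its median gives two halves the size of the arms, and the upper half should hold more psilocybin recipients. Aim 2c then compares drinking between those halves, which resembles an informal look at efficacy in a trial that plans no formal one.

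The contrast with the rest of the protocol sharpens the point. The stage 2 check in Section 3.3.13 names its timing, its performer and the quantities returned: error variance and drop-out. Section 4.5.4.3 first reviews drinking with the arms combined. Section 3.3.8.1.3 has the MEQ scored by staff outside the treatment team. Section 3.3.12.8 has no comparable control, while Section 3.3.13 still allows protocol changes, a revised sample size, and an interim efficacy analysis at the request of the sponsor or the DSMB. If SCQ-by-drinking results reached therapists, assessors or those making these decisions before the week-36 data were locked, conduct or self-report could be affected. A misleading signal could do this as readily as a true one.

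**Working it through.** Section 3.3.12.8 contains no sample size, alpha or power, so it has no figure to reproduce. The check asks how well the split tracks arm, what a gap would mean, and whether anyone who matters would see it.

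**Inputs.** Allocation is 1:1 (3.3.1). The pilot reported "MEQ scores ranging from .02 to .77 in the first session", with everyone on psilocybin (3.3.3.2). In Figure 3d, week-4 MEQ correlated r = -.884 with change in percent drinking days (n = 9); the Fisher 95% interval is tanh(atanh(-.884) ± 1.96/√6) = -.975 to -.532. No control-arm SCQ data are given, so the separation k, in psilocybin-arm SDs, is assumed to be 1, 2 or 3.

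**Agreement with arm.** Take SCQ ~ N(k, 1) on psilocybin and N(0, s²) on control. The pooled median is at ks/(1+s), so agreement = Φ(k/(1+s)).

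**What a true arm effect would show.** If the SCQ is unrelated to drinking within arm, the split shows (2 × agreement - 1) of the arm effect. For an effect size I use the one that a single-df test detects with power 0.8 under the inputs of Section 3.3.12.7 (N = 171, four predictors): f² = .046, or 2√f² = 0.431 SD. The stated f² = .065, read as the arm effect alone, would give power 0.91 rather than the stated 0.8, so I do not use it here.

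**What no arm effect would show.** If the SCQ correlates with drinking change only within the psilocybin arm, the gap is 2|r|φ(k/(1+s)) SD.

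With equal SDs (s = 1):

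| k | Agreement | Share shown | Gap, arm effect 0.431 SD | Gap, no effect, r = -.884 | Gap, no effect, r = -.532 |
|---|---|---|---|---|---|
| 1 | 0.691 | 0.383 | 0.17 | 0.62 | 0.37 |
| 2 | 0.841 | 0.683 | 0.29 | 0.43 | 0.26 |
| 3 | 0.933 | 0.866 | 0.37 | 0.23 | 0.14 |

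With control SD half the psilocybin SD, agreement is 0.748, 0.909 and 0.977. With a quarter it is 0.788, 0.945 and 0.992, and the no-effect gap at r = -.884 is 0.51, 0.20 and 0.04.

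**Noise.** After stage 2 there are 20 + 80 = 100 randomized. The standard error of the gap is √(1/50 + 1/50) = 0.20 SD.

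**Reading.** Over most of this range, a gap of a given size is as compatible with no treatment effect as with one. Only when control scores sit tightly at the floor and k is large does the split come close to arm. The conclusion therefore cannot rest on the weakness of the proxy alone.

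**Who would learn what.** Set against 3.3.12.8:
- Therapists attend the drug sessions (3.3.8.1.3, 3.3.8.2), rate behaviour during them (3.3.10.6.1), and guess the drug with a confidence rating afterwards (3.3.10.10). Those are participant-level cues; a group median split adds little to them.
- The SCQ and the Time-line Follow-back are both collected by the trial (Table 1), held in a database open to approved staff (3.3.11), and reviewed among team members (3.3.14.6). The ancillary work gives trial staff no data they lack.
- The variable shared is drinking days. The primary outcome is percent heavy drinking days (3.3.2).
- Section 3.3.13 ties the sample size check to error variance and drop-out, neither of which is an SCQ-by-drinking gap.

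**The case for a change.** The strongest reply is that silence is not a safeguard. Nothing in 3.3.12.8 bars the results from reaching trial staff, and a tabulated gap with an estimate is more persuasive than scattered individual scores. The protocol protects comparable information elsewhere, so one sentence here would be cheap. The access rules in Sections 3.3.11 and 4.2.2.2 govern data and materials, not interim findings.

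All of that is accurate as a description of the text. What it does not show is harm from following the plan as written. Harm needs two further events that the document does not describe: the analyses run before the week-36 lock, and the results reach people who treat, assess or decide. "Interim" is undated and could fall after week 36. No arm comparison is made and no alpha is spent, so the most that remains is a conditional risk of informal leakage.

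The obvious stronger remedy is also a poor bargain. Holding Aims 2c and 3 until lock could delay part of a dissertation for a long time. Letting Aim 2d proceed from a separate SCQ extract would not keep the SCQ apart from drinking, because both extracts would carry SCS-SF scores. Assuming integer totals with SD 9, correlation 0.8 between visits and 100 participants, about 85% have a unique SCS-SF pattern over two visits and 99% over three, so the files could be rejoined.

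**Conclusion.** The observation is right: data that include the SCQ are not fully blind, and 3.3.12.8 gives no data cut and no list of recipients. It does not call for a change. Those are details that the team fixes when releasing an extract, and the SAP may already cover them. As written, uncoded data go one way to an outside student, on a variable that is not the primary outcome, while trial staff already hold the same data and stronger cues to assignment. The primary analysis, its error rate and the sample size are untouched.

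On size, the split would agree with arm in roughly 69% to 93% of participants with equal SDs, and in up to 99% with control scores at the floor. With equal SDs, an arm effect of 0.431 SD would show as a gap of 0.17 to 0.37 SD, against 0.14 to 0.62 SD with no effect at all, and a standard error of 0.20 SD at 100 participants.

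These figures rest on an assumed SCQ separation, normal scores, and a pilot correlation from the MEQ (43 of the SCQ's 100 items) in nine open-label participants. The conclusion rests more on the absence of any stated route back to trial staff. It would need another look if the student also treated or assessed participants, or if results were circulated before lock.

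### Ancillary Aims 2c and 2d cut the SCQ at its median although the full scores are available; if the relation with change is roughly linear, this discards about 36% of the information for normal scores

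*Combined protocol and SAP*

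**What the plan says.** Section 3.3.12.8 describes work for a doctoral dissertation: "Additional ancillary interim analyses will be performed on blinded, de-identified data". Aim 2c takes the within-person change in drinking days, and Aim 2d the change in self-compassion. Each asks whether the changes "are greater in participants that score above the median on the SCQ than those with SCQ scores below the median score".

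Three other statements bear on the point.

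- The analyst gets scores, not high/low groups: "Blinded, de-identified scores on the SCQ, Self-Compassion Scale Short-Form (SCS-SF), and number of self-reported drinking days will be shared".
- Aim 3 of the same section uses the SCQ with no cut stated: "To examine whether SCS-SF scores mediate the relationship between SCQ scores and drinking behavior".
- Both arms are pooled. Aim 1 of the section describes participants "following two drug administration sessions (either psilocybin or placebo", and the data are blinded.

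Section 3.3.10.6.1 says of the SCQ: "This 100-item questionnaire has been used extensively to measure mystical-type states of consciousness". With 100 items, its score takes many values. Section 3.3.12.8 does not define which SCQ score is meant. It gives no reason for the median, no continuous-score version of Aims 2c and 2d, and no sample size, effect size, alpha or power for them.

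**The concern.** Aims 2c and 2d ask whether people with a stronger session experience change more. A median split answers this with a two-group comparison. It treats everyone above the cut as alike and everyone below it as alike, and it separates two people on either side of the cut however close their scores are. The cut point is also a property of the sample, so the contrast has no fixed meaning elsewhere. If change rises steadily with the SCQ, ignoring the spread within each half widens the confidence interval and lowers power, although the discarded detail is already in the analyst's hands.

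What is at stake is modest: the precision of two ancillary comparisons, and whether Aims 2c and 2d are on the same SCQ scale as the ancillary Aim 3.

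**Working it through.** The documents state no power for Aims 2c and 2d, so there is no figure of theirs to reproduce. The check asks how much a median split costs under stated assumptions.

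**Inputs**

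- Effect size: f² = .065 from section 3.3.12.7. There it belongs to the main Aim 2 treatment contrast. It is borrowed here, as an assumption, for a moderate effect.
- Alpha: 0.05 two-sided, also from section 3.3.12.7 and assumed to apply.
- Sample size: 171 is the planned 180 less 5% attrition (180 × 0.95 = 171), the most these aims could have on that attrition. The analyses are interim, so smaller values matter: 100 is the main-trial total after Stage 2 (20 + 80) and 20 is Stage 1 (section 3.3.13).
- Score shape: unknown. For psilocybin participants the only guide is the pilot (section 3.3.3.2): "Intensity of effects varied markedly from patient to patient, with MEQ scores ranging from .02 to .77 in the first session". Control scores are assumed.

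**Step 1. Correlation.** r = √(f² / (1 + f²)) = √(.065 / 1.065) = 0.247.

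**Step 2. What the split keeps.** With a linear relation, replacing the score by its above/below-median indicator multiplies the correlation by c = corr(score, indicator). The information kept is c². For a normal score c = √(2/π) = 0.798 and c² = 0.637, so 36% is lost. The split would need π/2 = 1.57 times as many participants for equal power.

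**Step 3. Power.** Noncentral F with 1 and N − 2 degrees of freedom and λ = N r² / (1 − r²), using r for the full score and c × r for the split.

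| Assumed score shape | c | Information lost | N = 100: full, split (points lost) | N = 171: full, split (points lost) |
|---|---|---|---|---|
| Normal | 0.798 | 36% | 0.71, 0.51 (20) | 0.91, 0.74 (17) |
| Half uniform on .02 to .77, half on 0 to .2 | 0.760 | 42% | 0.71, 0.47 (24) | 0.91, 0.70 (21) |
| Half uniform on .02 to .77, half on 0 to .4 | 0.805 | 35% | 0.71, 0.52 (19) | 0.91, 0.75 (16) |
| Two normal arms 3 SD apart | 0.864 | 25% | 0.71, 0.58 (13) | 0.91, 0.81 (10) |

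**Step 4. Where the loss shrinks** (normal scores, same formula).

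| True r | N | Full | Split | Points lost |
|---|---|---|---|---|
| 0.247 | 20 | 0.19 | 0.14 | 5 |
| 0.10 | 100 | 0.17 | 0.12 | 4 |
| 0.35 | 171 | 0.998 | 0.97 | 3 |
| 0.50 | 100 or 171 | about 1 | 0.99 or more | 1 or less |

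A small sample does not protect by itself. In simulation at N = 20 with true correlations of 0.44 to 0.66, the loss was 18 to 24 points.

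**Step 5. Other shapes.** Information lost is 25% for a uniform score, 19% and 14% for arms 4 and 5 SD apart, and 52% for an exponential score. If change really jumps at the median and is flat on either side, the split loses nothing.

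**The case against.** The strongest reply is that any headline power loss is built on borrowed inputs. That stands. The f² is not an SCQ correlation, the interim sample size is not given, and Step 4 shows losses of 5 points or less under other plausible inputs. A reader might infer a fixed cost of 10 to 20 points; the documents do not support an unconditional figure. The only related correlations they report are the pilot's, between session intensity (MEQ or HRS, not SCQ) and change in drinking, with absolute values of .71 to .88 in nine people. If correlations were truly that large, power would be near 1 either way at the larger sample sizes.

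Three further readings are tempting and do not hold.

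- *The pooled median sits near the bottom of the psilocybin range.* The documents contain no control-arm SCQ scores. Under the assumed control ranges 0 to .2 and 0 to .4, 19% and 33% of psilocybin participants fall below the median. Section 3.3.8.1.2 expects diphenhydramine to have noticeable effects that might be taken for psilocybin.
- *A continuous slope would isolate the effect of intensity.* In pooled, blinded data it still mixes differences between arms with differences within them. With arms 3 SD apart, 1.5² / (1.5² + 1) = 69% of the SCQ variance lies between arms. With the 0 to .2 control range it is 46%.
- *The trial would miss an intensity gradient in drinking.* The trial's own Aim 3 (section 3.3.12.4) uses the MEQ total and three 5D-ASC dimensions uncut against drinking outcomes, and the ancillary Aim 3 relates SCQ scores to drinking with no cut stated.

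None of this supplies a reason for the median cut.

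**Conclusion.** The point holds as a cheap improvement. The median split is the stated comparison for both aims, it is unexplained, and the full scores are in hand. Given a roughly linear relation, it discards about 36% of the information for normal scores and about 25% to 42% across the two-arm mixtures in the table. With an assumed true correlation of about 0.25 and 100 to 171 participants, that is about 10 to 24 points of power. The figure depends on those assumptions: it drops to a few points for very weak correlations, for strong ones at those sample sizes, and for a moderate correlation in a very small sample. It is zero for a step at the median.

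The scope is narrow. The trial's Aims 1 to 5, its primary and secondary outcomes and its sample size are untouched.

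**What to change.** In section 3.3.12.8, restate Aims 2c and 2d as a regression of the post-intervention value (drinking days; SCS-SF score) on the SCQ score as a continuous variable, adjusted for the pre-intervention value. Report the slope, for example per SD of SCQ, with its 95% confidence interval. Check linearity with a plot or a spline term. Keep the above- and below-median means for display only. Name the SCQ score to be used. Add a sentence saying that, because the arms are pooled and blinded, the slope combines between-arm and within-arm differences and is not a pure intensity effect.

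The essential change is to leave the SCQ uncut; the baseline adjustment is a conventional way to analyse change and is a separate choice. The cost is a few sentences, with no new data, participants or unblinding. The small downside is that a single slope assumes approximate linearity, which the plot or spline is there to check.
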